8 RESEARCH QUESTION AND OBJECTIVES

This study aims to determine the prevalence of patients treated with alglucosidase alfa with significant hypersensitivity/anaphylactic reactions who undergo immunology testing. The difference in prevalence of testing between the two periods of 3 years before and after the implementation of the revised SIP (version 8.2) will be assessed as a measure of effectiveness of risk minimization measures.

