9.4 DATA SOURCES

This study is based on secondary analysis of existing data sources.

The following data sources will be considered:

- Genzyme's Pharmacovigilance adverse event database,
- Genzyme Clinical Specialty Laboratory database.

Reports pertaining to the same patients will be linked across databases using date of birth, initials, and country of origin.

The Genzyme's Pharmacovigilance adverse event database will provide information about patients with a reported significant hypersensitivity /anaphylactic reaction.

The Genzyme Clinical Specialty Laboratory database will provide history of records and results of immunology testing conducted in these laboratories for patients treated with alglucosidase alfa.

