9.7 DATA ANALYSIS

The analyses will be descriptive and will be made on all patients available in the databases at time of each analysis.

9.7.1 Analysis population:

The primary analysis population will be patients with spontaneously reported significant hypersensitivity/anaphylactic reaction while treated with alglucosidase alfa treatment course in countries in Europe. Patients will be divided by following two groups:

Group 1 (pre-SIP):

- Patients with hypersensitivity/anaphylactic reaction event onset date from 01 September 2012 to 31 August 2015

Group 2 (post-SIP):

 Patients with hypersensitivity/anaphylactic reaction event onset date from 01 October 2015 to 30 September 2018

9.7.2 Determination of patient status on immunology testing:

A patient in Group 1 (or 2) will be considered having undergone any immunology testing (immunology test = Yes) for the respectively period if one of the two conditions is met:

- i) a valid test result is available for at least one of the following tests from Genzyme Clinical Specialty Laboratory database
 - a. alglucosidase alfa IgE antibody,
 - b. alglucosidase alfa IgG antibody,
 - c. complement activation,
 - d. serum tryptase
- ii) the test date is after the alglucosidase alfa treatment start date through the end of the period cutoff (31 August 2015 for Group 1 and 30 September 2018 for Group 2)

Note that patients without a valid test meeting above criteria will be considered without having immunology test performed (immunology test=No). Therefore, there is no missing data for this endpoint.

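### Section 9.7.2 scores a patient whose only laboratory samples failed or were pending as not tested, and its lead-in contradicts its own Note; the effect on any testing is probably small

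*Protocol*

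**What the plan says.** Protocol section 8 sets the target as the "prevalence of patients treated with alglucosidase alfa with significant hypersensitivity/anaphylactic reactions who undergo immunology testing". The difference between the two 3-year periods "will be assessed as a measure of effectiveness of risk minimization measures".

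Section 9.7.2 turns this into a Yes/No status. Its lead-in credits a patient with testing "if one of the two conditions is met". Those two conditions are:

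- Condition (i), on the result: "a valid test result is available for at least one of the following tests from Genzyme Clinical Specialty Laboratory database". The four tests are IgE, IgG, complement activation and tryptase.
- Condition (ii), on timing: "the test date is after the alglucosidase alfa treatment start date through the end of the period cutoff". For Group 1 the cutoff is 31 August 2015; for Group 2 it is 30 September 2018.

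The Note that follows says that "patients without a valid test meeting above criteria will be considered without having immunology test performed (immunology test=No", and concludes that the endpoint therefore has no missing values.

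On the data, section 9.4 says that the laboratory database will provide the "history of records and results of immunology testing conducted in these laboratories". Section 9.9 speaks more narrowly of results only. The one cause of under-counting that it names is testing done outside the Clinical Specialty Laboratory.

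**The concern.** The objective concerns what physicians do after a reaction: whether the patient is tested. Whether a sample then yields a valid, released result depends on handling, assay and turnaround. The Note merges two different patients: one for whom no sample was sent, and one whose sample was sent but gave no usable result by the time of analysis. Both are labelled as having had no test performed. For the second patient that label is wrong, and the claim of no missing data holds only because the unknowns have been recoded as No.

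None of the prevalence summaries in 9.7.5 uses a titer or any other result value. They count patients tested and types of test performed, so validity of the result is not needed for the endpoint.

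Two things are at stake: a prevalence that is somewhat too low for a reason that 9.9 does not disclose, and a rule that two programmers could code differently because the lead-in and the Note disagree.

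**Working it through.** **1. The two readings of 9.7.2, side by side.**

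| Patient | Lead-in read literally (i or ii) | Note (valid test meeting the criteria) | Tested in the window? |
|---|---|---|---|
| Valid result dated in the window | Yes | Yes | Yes |
| Only failed or pending samples, test date in the window | Yes, through ii | No | Yes |
| Valid result dated only after the cutoff | Yes, through i | No | No |
| No sample | No | No | No |

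The readings disagree in rows 2 and 3. The Note gives the wrong status in row 2, and the literal lead-in gives the wrong status in row 3. Neither matches the objective throughout. Joining the conditions by 'and' repairs row 3. Row 2 is repaired only by also dropping the requirement of a valid result.

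**2. The plan's own figures.** Table 3 (section 9.5) shows prevalence from 50% to 95%. At n = 100 and 85%: 0.85 ± 1.96 × √(0.85 × 0.15 / 100) = 0.85 ± 0.070, which gives 78.0% to 92.0%, as printed. All 15 normal-approximation cells reproduce to 0.1 point. The five exact cells at n = 50 agree to within 0.1 point. No cell depends on how a Yes is defined, so none changes.

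**3. Size of the under-count.** Let P be the true prevalence of testing at this laboratory, and f the share of tested patients who have no valid available result of any of the four types in the window. Then

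observed prevalence = P × (1 − f), and under-count = P × f.

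The documents give no f; the values below are assumptions.

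| P | f = 1% | f = 2% | f = 5% |
|---|---|---|---|
| 50% | 0.50 | 1.00 | 2.50 |
| 85% | 0.85 | 1.70 | 4.25 |
| 95% | 0.95 | 1.90 | 4.75 |

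(Percentage points.)

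**4. Why f is likely to be small for any testing.** A single valid result since treatment start gives a Yes. If samples failed independently at 5% (an assumption), a patient with one sample would be missed 5% of the time, with two samples 0.05² = 0.25%, and with three 0.05³ ≈ 0.01%. A count for one test type has fewer samples behind it and less of this protection.

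**5. Effect on the difference between periods.**

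observed difference = P₂(1 − f₂) − P₁(1 − f₁).

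- Equal f: this is (P₂ − P₁)(1 − f). No difference is created; a true 10-point rise reads as 9.8 points at f = 2% and 9.5 at f = 5%.
- Unequal f with no true change: the result is −P(f₂ − f₁). At P = 85% with f = 2% before and 5% after, that is −0.85 × 0.03 = −2.55 points.

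For scale, the 95% half-width of the difference at 85% is 1.96 × √(2 × 0.85 × 0.15 / n): 9.9 points at an assumed 100 patients per group and 5.7 at an assumed 300.

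**The case against.** The strongest reply is that the rule is a reasonable operational choice. A valid result is objective and reproducible, and it keeps cancelled or erroneous entries out of a secondary-data study. A statistical analysis plan, not shown here, could define validity and say how pending samples are handled. The error also needs a patient with no valid result of any type over the whole treatment history. These arguments bear on size, and they stand. They do not make the Note's label true, nor do they reconcile the lead-in with the Note.

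A second reply also stands in part. It is not established that the database logs samples that were received but failed or were queued. Sections 9.2 and 9.4 mention records as well as results; 9.9 mentions results only. The fix therefore has to be conditional on what is held.

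A reader might go further and infer that pending results bias the comparison against the revised SIP, because the Group 2 cutoff coincides with the end of data collection on 30 September 2018. The documents do not support that. Condition ii limits the test date and not the date of release. Section 9.7 uses what is in the databases at the time of each analysis, no extraction date is given, and the final report is due in December 2018. Results released after the cutoff could still count. Nor does any passage report a change in assay, shipping or turnaround between the periods.

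**Conclusion.** The point holds in limited form. As its Note is written, 9.7.2 records some tested patients as not tested, and the lead-in contradicts the Note. Section 9.9 does not disclose this source of under-counting.

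The size is unknown. At 85% prevalence it is 0.85 to 4.25 points for an assumed patient-level f of 1% to 5%, and for any testing f probably lies low because one valid result is enough. By-type counts are more exposed, provided they follow the same rule, which 9.7.5 does not say. A spurious difference between periods needs f to differ between them; nothing in the protocol shows that it does. The tempting conclusions that prevalence is materially understated, or that the before/after comparison is distorted, go beyond the documents.

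**What to change.** - Reword the lead-in of 9.7.2 so that the conditions are joined by 'and'.
- Where the laboratory database holds such records, replace the requirement of a valid result by any Clinical Specialty Laboratory test record for one of the four tests, with a test or collection date in the window, whatever the result status. State which date is used.
- Report the proportion with a valid result by period and test type, as a secondary or sensitivity row.
- If the database holds results only, keep the valid-result rule (still with 'and'), delete the statement that there are no missing data, and add this under-count to 9.9.

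The cost is a rewording and one extra row per table, from a database that the sponsor holds, after a check of which records it contains. The small downside is that the main figure may include samples that gave no usable result; the secondary row shows how many.

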9.3 VARIABLES

The following variables will be considered for the analysis.

The characteristics of patients with a reported significant hypersensitivity /anaphylactic reaction (if available):

- age
- gender
- weight
- description of hypersensitivity/anaphylactic reactions
 - nature of event
 - outcome
 - seriousness
 - medically confirmed
 - event date
 - event severity
 - mild, moderate, severe
 - grade 1 to 5 according to NCI Common Terminology Criteria for Adverse Events
- history of hypersensitivity/ anaphylactic reactions
- history of reported drug exposure

The characteristics of alglucosidase alfa treatment course (if available):

- treatment start date
- number of doses received
- treatment dosage received

The history of immunology testing performed since treatment start:

- any immunology testing
- alglucosidase alfa IgE antibody
- complement activation
- serum tryptase
- alglucosidase alfa IgG antibody

Immunology testing results will be generally reported as titers.

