9.9 LIMITATIONS OF THE RESEARCH METHODS

The limitations of the current study are related to the characteristics of the data sources. In Genzyme's Pharmacovigilance adverse event database only information reported in documentation of spontaneous reports will be available and missing data may be observed with a different range of frequency for each variable. But all patients' characteristics will be

described when available. High frequency of missing data in some characteristics may limit the possibility to define relevant subgroups of patients with sufficient numbers.

In the Genzyme Clinical Specialty Laboratory database only results of immunology testing conducted in the Clinical Specialty Laboratory will be available. Thus, this may lead to an underestimation of the real prevalence of immunology testing conducted by physicians in the routine practice.

In the absence of a common patient identifier, linkage of these two databases will be conducted by matching of available common patients characteristics from the two data sources but all efforts will be made including manual checks of available data sources to avoid any potential erroneous linking.

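### Section 9.7.2 scores patients who cannot be linked to the laboratory database as untested, then declares that the testing endpoint has no missing data

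*Protocol*

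**What the plan says.** Patients are identified in the pharmacovigilance database, and their testing history is taken from the sponsor's own laboratory database (protocol, sections 9.2 and 9.4). The two are joined on date of birth, initials and country of origin.

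Section 9.7.2 sets the status rule. A patient counts as tested "if one of the two conditions is met". Condition (i) is that "a valid test result is available for at least one of the following tests from Genzyme Clinical Specialty Laboratory database". Condition (ii) is that "the test date is after the alglucosidase alfa treatment start date through the end of the period cutoff". The note below the rule says that "patients without a valid test meeting above criteria will be considered without having immunology test performed (immunology test=No"), and then: "Therefore, there is no missing data for this endpoint".

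Section 9.9 says of the pharmacovigilance data that "missing data may be observed with a different range of frequency for each variable". On the join it says: "In the absence of a common patient identifier, linkage of these two databases will be conducted by matching of available common patients characteristics". It promises manual checks against erroneous links. It also discloses that only tests run in the sponsor's laboratory are visible, so true prevalence may be underestimated. Section 9.3 collects the treatment start date only where it is available.

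Section 9.7.5 compares the two periods by a difference of proportions with a 95% confidence interval. Section 8 makes that difference the measure of how well the revised safety information packet worked.

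**The concern.** A Yes needs a successful link. A No needs only that no qualifying record was found. The rule therefore puts two different patients in one category: one whose laboratory history was searched and held no test, and one whose history could not be searched because the report lacked the matching fields. The second patient's outcome is missing, and the rule fills it in as No.

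The error runs one way, because a missed link can turn a true Yes into a No but never the reverse. It carries into the pre/post difference, and a change between periods in the completeness of spontaneous reports would look like a change in testing. A regulator reading the result could not tell the two apart, since the protocol provides no category in which linkage failures would show.

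A second problem lies in the same rule. The lead-in asks for one of two conditions, while the note asks for a valid test that meets the criteria above, and the period cutoffs have no effect unless the date condition binds. If both conditions are required, a laboratory result for a patient with no recorded start date cannot qualify, and that patient also becomes No.

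**Working it through.** **The plan's own figures.** Table 3 (section 9.5) is the only numerical planning material. For 100 patients at 75%: 0.75 ± 1.96 × √(0.75 × 0.25 / 100) = 0.75 ± 0.085, or 66.5% to 83.5%, as stated. In all, 19 of the 20 cells reproduce to 0.1 point, using the normal approximation for 100, 200 and 300 patients and Clopper-Pearson for 50. The exception (50 patients, 95%) gives an upper limit of 99.2 against 99.1, which is immaterial. These intervals express sampling error only.

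**Inputs for the bias.** True prevalence p is taken from the range in Table 3. Capture s is the share of truly tested patients who end up as Yes. The protocol gives no value for s, so 70% to 90% is assumed.

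**Effect on one prevalence.** With no false matches, observed = p × s.

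| True p | s = 90% | s = 80% | s = 70% |
|---|---|---|---|
| 75% | 67.5% | 60.0% | 52.5% |
| 90% | 81.0% | 72.0% | 63.0% |

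**Effect on the difference.** Observed difference = p₂s₂ − p₁s₁.

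- Equal capture of 80%, true 75% to 90%: 72.0 − 60.0 = 12 points seen, against 15 true.
- No true change (75% in both periods), capture 70% then 90%: 67.5 − 52.5 = +15 points, all false.
- No true change (75%), capture 80% then 90%: 67.5 − 60.0 = +7.5 points. In the opposite order: −7.5 points.
- True 75% to 90%, capture 90% then 70%: 63.0 − 67.5 = −4.5 points, so a real rise is reversed.

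**What the planned interval would show.** For the false +15 points with 100 patients per period:

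- SE = √(0.525 × 0.475 / 100 + 0.675 × 0.325 / 100) = 0.0685.
- 95% CI = 0.150 ± 1.96 × 0.0685, or 1.6 to 28.4 points.
- The chance that such an interval excludes zero is Φ(0.150/0.0685 − 1.96) + Φ(−0.150/0.0685 − 1.96), about 59%.
- With 200 per period the interval is 5.5 to 24.5 points and the chance about 87%. More patients make the false finding more likely.
- For the false +7.5 points with 100 per period, the interval is −5.8 to 20.8 and the chance about 20%.

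**What separate reporting would show.** Assume 100 patients, 20 who cannot be linked, and 75% tested among the other 80, which is 60 patients.

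- Present rule: 60/100 = 60%.
- Linkable patients only: 60/80 = 75%.
- All unlinkable counted as tested: (60 + 20)/100 = 80%.

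The 15-point gap between the first two exceeds the 8.5-point half-width in Table 3. With 5, 10 or 30 unlinkable patients, the all-No to all-Yes range is 71.3% to 76.3%, 67.5% to 77.5%, or 52.5% to 82.5%. If both periods looked like the 20-patient case, the bounds on the difference would be 60 − 80 = −20 and 80 − 60 = +20 points.

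**The case against.** The best defence has five parts.

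- **The analysis is descriptive, and linkage tables are often left to the SAP.** This is true of the tables. But the protocol itself fixes the imputation and asserts that nothing is missing, and the difference is its stated measure of effectiveness.
- **Matching uses whatever characteristics are available, and linkage and its quality control are documented (sections 9.6, 9.8, 9.9).** This stands in part. A reader might infer that a report lacking one key can never be matched. The text does not say so, because partial matching with manual checks remains possible. But the stated aim of the checks is to avoid erroneous links. Missed links are not discussed, and documenting them does not change how they are scored.
- **Outside-laboratory testing is already disclosed, with its direction.** This stands. A reader might infer that the protocol hides this source of underestimation, and it does not. A not-determinable status would not cure it either: a patient with complete keys who was tested elsewhere would still count as untested.
- **A missing start date does not necessarily force No.** This stands on the literal wording, where condition (i) alone is enough. It is tempting to state as fact that patients without a start date are scored untested. That follows only if both conditions are required, as the note and the cutoffs suggest. What is established is the contradiction.
- **Dropping undeterminable patients from the primary denominator carries its own bias.** This also stands. If fuller reports come from places that test more, the restricted estimate is too high. So the restricted analysis belongs beside the present rule and need not replace it.

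**Conclusion.** The no-missing-data statement is wrong in substance. For patients who cannot be linked, unknown status is imputed as No, and section 9.9 does not disclose this. Missed links lower each prevalence in proportion to capture. Equal capture in the two periods only shrinks a real difference; unequal capture can create, enlarge or reverse one.

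A reader might go further and conclude that the study will report a false change. The documents do not support that: they give no linkage or capture rate and no evidence that capture differs between periods. The sizes (12 points seen for 15 true, and a false +15) rest on assumed capture of 70% to 90%, a true prevalence chosen from the Table 3 range, and no false matches, which would push prevalence the other way. What is certain is the scoring rule, the direction of the error from missed links, and a confidence interval that carries neither. The conflict over the two conditions in section 9.7.2 is a separate, definite defect.

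**What to change.** In section 9.7.2:

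1. Delete the sentence that claims no missing data.
2. Reconcile the wording so that both conditions are required: a valid result for at least one listed test, dated after treatment start and on or before the period cutoff.
3. Use three statuses. Tested: both conditions met. Not tested: all linkage keys present, laboratory database searched, no qualifying test found. Not determinable: a linkage key missing so that no match could be settled, or a laboratory result found whose date cannot be judged because the start date is missing.

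In section 9.7.5:

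4. Report the not-determinable count by period and country.
5. Keep the present all-patients rule as the lower bound for each prevalence. Add a linked-only analysis and an all-Yes bound. Linked-only must mean patients whose keys allowed a search; restricting to those with a laboratory record would remove the untested.
6. Do the same for the difference. Its lower bound is post all-No minus pre all-Yes, and its upper bound is post all-Yes minus pre all-No.

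In section 9.9:

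7. State that missed links lower prevalence, and that outside-laboratory testing remains uncaptured and may differ between periods.

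The cost is one derived variable, one extra table and a wider range of reported results. If the not-determinable counts prove small, the range will be narrow and the present estimate stands on firmer ground.

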9.7.3 Demographic and baseline disease characteristics

Patient demographics and baseline disease characteristics will be summarized using descriptive statistics: number of observations (n), mean, median, standard deviation (SD), minimum, and maximum. Categorical variables will be summarized using frequencies and percentages. Denominator will be based on the number of patients in the analysis population as defined in Section 9.7.1.

Following variables will be summarized by Group (1 or 2):

- patient characteristics (age, gender, weight, country/region)
- history of hypersensitivity/anaphylactic reactions

9.7.4 Alglucosidase alfa treatment information and the details on hypersensitivity/anaphylactic reaction event

Following alglucosidase alfa treatment information will be summarized by group as well as the combined analysis population:

- time from treatment initiation to first onset of hypersensitivity/anaphylactic reactions event within the study period
- number of doses received prior to first onset of hypersensitivity/anaphylactic reactions event within the period

The details of the hypersensitivity/anaphylactic reactions event reported in each of the periods will be summarized by intensity, seriousness (SAE or not) of the event, and relationship to alglucosidase alfa treatment, respectively. The summaries will be provided by analysis group (1 and 2). For multiple events occurred in the same study period, patients will be counted only once and only the event with the worst category will be considered for the corresponding

analysis. Corresponding listing will be provided with detailed information collected in the database

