All patients available in the study population will be considered for the analysis. No assumption will be made on the expected number of patients.

Data analysis

The primary analysis population will be patients with spontaneously reported significant hypersensitivity/anaphylactic reaction while treated with alglucosidase alfa treatment course in countries in Europe. The analyses will be descriptive and will be made on all patients available in the databases at time of each analysis.

The prevalence of testing will be provided for each period (3-year period before and 3-year period after implementation of the revised SIP). The difference in prevalence rate between two groups will be calculated, with corresponding 95% confidence interval calculated based on normal approximation of two proportions.

The results will be displayed by 3-year period before and after the implementation of revised SIP and by age, gender and country in Europe when appropriate.

Milestones

Annual analyses will be conducted over a 3-year period starting one year after implementation of the revised SIP in Europe. The implementation of the revised SIP may be started from 01 September 2015 after completion of pre-updated SIP data collection.

The first report will be prepared in December 2016, based on data gathered up to one year after implementation of the revised SIP (from 01 October 2015 to 30 September 2016) and will also include results for the 3-year period before implementation of the revised SIP (from 01 September 2012 to 31 August 2015).

The second report prepared in December 2017 will add data gathered in the second year after implementation of the revised SIP (from 01 October 2016 to 30 September 2017) and the final report prepared in December 2018 will include cumulative data for both periods (from 01 September 2012 to 31 August 2015 and from 01 October 2015 to 30 September 2018).

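### At the two interim reports, the worst-event tables set 36 pre-SIP months against 12 or 24 post-SIP months, which can make post-SIP reactions look milder

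*Protocol*

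**What the plan says.** Protocol section 9.7.4 states that details of the reactions "will be summarized by intensity, seriousness (SAE or not) of the event, and relationship to alglucosidase alfa treatment, respectively". Both groups are shown, so they can be read against each other. For patients with several reactions the rule is "For multiple events occurred in the same study period, patients will be counted only once and only the event with the worst category".

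For two other variables the same section uses the first event instead: time from treatment start to first onset, and "number of doses received prior to first onset of hypersensitivity/anaphylactic reactions event within the period".

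The Synopsis (Milestones) sets the data behind each report. On the post-SIP side, the first report uses "data gathered up to one year after implementation of the revised SIP (from 01 October 2015 to 30 September 2016"). On the pre-SIP side it already shows the full three years, 01 September 2012 to 31 August 2015. The second report "will add data gathered in the second year after implementation of the revised SIP (from 01 October 2016 to 30 September 2017"). Only the final report has the full three years on each side.

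Section 9.7 says the analyses are made on the patients in the databases at the time of each analysis. Section 9.6 says the combined extractions serve both interim and final analyses. No section shortens the pre-SIP window at the interims, and section 9.9 does not list unequal windows as a limitation.

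**The concern.** The worst of a patient's events within a window can only stay the same or get worse as the window lengthens. A worst-event percentage therefore depends on how severe each reaction is and also on how long patients were observed. With equal windows the second part cancels between groups. At the interims it does not: Group 1 has three times the window of Group 2 in the first report and one and a half times in the second. Dividing by the number of patients does not correct this, because the extra time changes each patient's category as well as the number of patients.

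Section 12 sends the interim reports to the agency, and the study is meant to measure the effectiveness of a risk minimisation measure. A lower share of severe or serious reactions after the revised SIP could be taken as a benefit, or as a difference in case mix between the groups, when it reflects only the shorter window.

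**Working it through.** **1. Window lengths, from the dates in the Synopsis and section 9.1 (both end dates counted).**

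- Pre-SIP, 01 September 2012 to 31 August 2015: 1095 days, 36 months.
- Post-SIP at the first report, 01 October 2015 to 30 September 2016: 366 days, 12 months.
- Post-SIP at the second report, to 30 September 2017: 731 days, 24 months.
- Post-SIP at the final report, to 30 September 2018: 1096 days, 36 months.

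This reproduces the plan's two 3-year periods. The pre:post ratio is 1095/366 = 3.0, then 1095/731 = 1.5, then 1095/1096 = 1.0.

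**2. Effect of window length on a worst-event share.** The documents give neither a recurrence rate nor a severe share, so both are assumed here. Let reactions in a patient follow a Poisson process with rate L per year. Let each be severe with probability s, independently of the patient's other reactions. A patient enters the table with at least one reaction in a window of T years. Then

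P(worst is severe | at least one reaction) = (1 − exp(−L·T·s)) / (1 − exp(−L·T)).

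For L > 0 and 0 < s < 1 this rises with T. Example with s = 0.3 and L = 0.5:

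- T = 3: (1 − exp(−0.45)) / (1 − exp(−1.5)) = 0.3624 / 0.7769 = 46.6%.
- T = 1: (1 − exp(−0.15)) / (1 − exp(−0.5)) = 0.1393 / 0.3935 = 35.4%.

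The gap is 11.2 points although s is the same in both periods.

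**3. Range at s = 0.3.** Gaps are in percentage points.

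| L per year | 36 months | 24 months | 12 months | Gap, first report | Gap, second report |
|---|---|---|---|---|---|
| 0.02 | 30.6% | 30.4% | 30.2% | 0.4 | 0.2 |
| 0.1 | 33.2% | 32.1% | 31.1% | 2.1 | 1.1 |
| 0.2 | 36.5% | 34.3% | 32.1% | 4.4 | 2.2 |
| 0.5 | 46.6% | 41.0% | 35.4% | 11.2 | 5.6 |
| 1 | 62.5% | 52.2% | 41.0% | 21.5 | 10.3 |

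**4. Sensitivity to the assumptions.**

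- *Correlated severity within a patient.* With a beta-binomial model at an assumed within-patient correlation of 0.5, the first-report gaps at 0.2, 0.5 and 1 per year fall from 4.4, 11.2 and 21.5 points to 2.1, 5.2 and 9.5. With full correlation every reaction in a patient has the same category and the gap is zero.
- *Uneven recurrence between patients.* With a gamma-mixed rate (shape 0.3) and s = 0.2, the share at a mean of 0.1 per year is 23.2% over 12 months and 28.4% over 36, a gap of 5.2 points. The plain Poisson model at the same s and rate gives 20.8% and 22.5%, a gap of 1.7. Uneven recurrence can therefore enlarge the gap at low mean rates.

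**5. Alternatives under the step 2 model.** The first event in the window is severe with probability s whatever T is, and so is the average event. Both summaries give the same expected share over 12, 24 and 36 months.

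**The case against.** The strongest reply is that nothing the study sets out to estimate is touched. The objective in section 8 is the difference in testing prevalence, and section 9.7.5 plans a difference and confidence interval for that only. Reaction details are tabulated by group without a difference or a test, and severity enters no planned subgroup. The artefact goes when both windows reach 36 months, and the interim dates are stated openly. No section lists the 9.7.4 tables as interim content. All of this stands and limits the weight of the point. The last item is an inference, but a reasonable one, because sections 9.6 and 9.7 apply the analyses to each report.

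A second reply is that the size is unknown. This also stands: with rare recurrence or strongly correlated severity the gap is negligible. The protocol does provide for several events per patient, so it does not treat recurrence as impossible.

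A third reply defends the worst-event rule. It is a coherent per-patient summary, and it fits a testing outcome that is also per patient and cumulative to the period cutoff. Replacing it at the interims would move each patient's most serious reaction out of the summary tables of a safety study and into a listing. This is a good reason to keep the table. It is not a reason to leave it as the only summary, and the planned listing does not correct the group percentages.

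A reader might go further and infer that post-SIP reactions must look milder by construction, or that the testing comparison is biased by this rule. The documents support neither. The first needs recurrent reactions whose severity varies within a patient, on which they give no data. The second does not follow, because the rule governs the reaction tables and not the counting of tests.

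**Conclusion.** The point holds as a minor one. The worst-event rule in section 9.7.4, combined with the interim windows in the Synopsis, gives side-by-side percentages that are not comparable at the first and second reports when reactions recur. The tendency is towards milder-looking post-SIP reactions. Under the stated assumptions the first-report gap runs from under half a point to about 21.5 points, and the second-report gap is about half of that. These figures illustrate a mechanism and are not estimates for this population. Correlated severity within patients pulls them towards zero, and uneven recurrence can raise them. Only descriptive tables in two interim reports are affected.

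**What to change.** In section 9.7.4, keep the worst-event table. For the two interim reports, add a summary of intensity, seriousness and relationship, either per event or on each patient's first event in the period, as the section already does for onset and doses. State that any pre/post reading of reaction details at the interims rests on that summary. Label the interim worst-event table as not comparable between groups because the windows differ (36 months against 12 or 24). The final report needs no change.

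The cost is one extra table per interim report, a little programming on data already extracted, and two sentences in the protocol.
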